8.6 Follow-up of subjects withdrawn from treatment

In case of withdrawal the patient will not be followed.

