8. METHODS

8.1 Study parameters/endpoints

8.1.1 Main study parameter/endpoint

Quality of recovery score (QOR-40 questionnaire) at 24 hours after extubation (appendix 1).

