8.2 Randomisation, blinding and treatment allocation

Randomisation:

Computer-generated randomization (supported by our statistician) will be used with stratification for center. To ensure a balanced distribution, we will use block randomization.

Blinding and treatment allocation:

Blinding of the surgeons to the level of NMB is ensured by covering the hand with the neuromuscular monitoring equipment under the sterile drapes and the nerve stimulator and computer are placed behind the sterile drapes away from the surgeons. All study medications are prepared (and labeled 'study medicine') by the anesthesiologist or his/her assistant after opening the envelope containing the allocation of treatment. This will be done in the operating room before the surgeons enter. Surgeons, scrub nurses, postoperative care nurses and the investigator assessing the postoperative endpoints are blinded to group allocation. The attending anesthetic staff in the operating room is not blinded.

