8.4 Withdrawal of individual subjects

Subjects can leave the study at any time for any reason if they wish to do so without any consequences. The investigator can decide to withdraw a subject from the study for urgent medical reasons.

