8.5 Replacement of individual subjects after withdrawal

Patients withdrawing will be replaced, with a maximum of 10 patients.

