10.1 Primary study parameter(s) and secondary study parameter(s)

For the primary analysis group A and B will be compared with regard to the primary end-point (QOR-40 score at day 1). Factorial ANOVA will be used to compare groups and to adjust for co-variates *i.e.* age, gender and side of nephrectomy. P-values < 0.05 will be considered statistically significant. All analyses will be performed on an intention-to-treat basis.

Study parameters/endpoints	Presentation of data (quantitative/qualitative)
Quality of recovery	Quantitative
Medication use	Quantitative
Pain	Quantitative
Surgical rating score	Quantitative
Nausea/vomiting	Quantitative
Surgical parameters	Quantitative
Evaluation of post-operative complications	Quantitative

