11.2 Recruitment and consent

At the Radboudumc and LUMC, respectively 90 and 45 laparoscopic donor nephrectomies are performed annually. All eligible donors will be screened. With an inclusion rate of approximately 80%, we expect that the screening (and inclusion period) will be 11 months.

Informed consent is obtained at least two weeks after providing written information about the study. During this two-week interval, an independent physician can be consulted for questions. At the day of hospital admission, one day before surgery, informed consent will be obtained. Then, one, unique number will be assigned (study number).

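### Section 8.6 ends follow-up for every withdrawn patient, so obtainable 24-hour QOR-40 scores are not collected and the intention-to-treat analysis lacks them; the bias is probably small and the fix is cheap

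*Combined protocol and SAP*

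**What the plan says.** Four short statements in the combined protocol and SAP have to be read together.

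- **Section 8.4** gives two routes out of the study. The subject may leave freely, or: "The investigator can decide to withdraw a subject from the study for urgent medical reasons". The second route does not depend on the patient refusing anything.
- **Section 8.5:** "Patients withdrawing will be replaced, with a maximum of 10 patients". It does not say whether the patient who was replaced remains in the analysis.
- **Section 8.6:** "In case of withdrawal the patient will not be followed". There is no exception. The heading speaks of withdrawal from treatment, whereas 8.4 speaks of the study.
- **Section 10.1:** "All analyses will be performed on an intention-to-treat basis".

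Timing comes from three other places. Under section 11.2, "At the day of hospital admission, one day before surgery, informed consent will be obtained". Under section 8.2, study medication is prepared in the operating room "after opening the envelope containing the allocation of treatment". Under section 8.1.1, the primary endpoint is the QOR-40 at 24 hours after extubation.

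**The concern.** The rule in 8.6 treats all withdrawals alike. For a patient who refuses further data collection, no follow-up is the ordinary consequence and is not at issue. The problem is the patient who does not refuse, chiefly one whom the investigator withdraws under 8.4. If this happens after the envelope is opened and before the 24-hour questionnaire, the primary outcome is missing because the protocol says so, not because it could not be obtained.

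An intention-to-treat analysis needs outcomes from the patients as randomised. Under 8.5 and 8.6 together, the scores available are those of completers plus replacements. A replacement is a different patient and cannot stand in for the score that was not taken. Medical reasons for early withdrawal may well go with poor recovery, which is what the QOR-40 measures. If such withdrawals also differ between arms, the comparison is biased, and a score never collected cannot be fully recovered by analysis. Withdrawals after 24 hours touch only the 48-hour and 4-week secondary endpoints.

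**Working it through.** **The plan's own figure.** Section 4.4 has a 10-point difference, SD 15, alpha 5% and 90% power. With two-sided alpha, n = 2 × (1.960 + 1.282)² × 15² / 10² = 47.3, so 48 per group, as stated. Power at 48 is 90.4% by the normal formula and 89.8% by the t-test.

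**Inputs that the documents do not give.** There is no expected withdrawal rate, no split by arm and no estimate of how much worse withdrawn patients would score. These are assumed below. I also assume that replacement brings each arm back to 48 completers.

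**Bias formula.** Let k be the number withdrawn before 24 hours in an arm and d the number of points by which they would have scored lower than completers. The completers' mean overstates the mean of everyone randomised to that arm by d × k/(48 + k). The bias in the comparison is the difference between arms:

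bias = d_A × k_A/(48 + k_A) − d_B × k_B/(48 + k_B)

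**False-positive rate.** SE = 15 × √(2/48) = 3.06. The test is a two-sided 5% t-test with 94 df, no true effect and no covariates. The rate comes from the noncentral t with noncentrality bias/SE.

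**Fractions.**
- 3:2 gives 3/51 − 2/50 = 0.0188.
- 7:3 gives 7/55 − 3/51 = 0.0684.
- 10:0 gives 10/58 = 0.172.
- For 5:5, each arm has 5/53 = 0.094.

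| Withdrawals before 24 h | Deficit (points) | Bias (points) | False-positive rate |
|---|---|---|---|
| 3:2 | 10 in both arms | 0.19 | 5.04% |
| 3:2 | 30 in both arms | 0.56 | 5.38% |
| 7:3 | 10 in both arms | 0.68 | 5.56% |
| 7:3 | 15 in both arms | 1.03 | 6.3% |
| 7:3 | 30 in both arms | 2.05 | 10.18% |
| 10:0 | 15 | 2.59 | 13.3% |
| 5:5 | equal in both arms | 0 | 5% |
| 5:5 | 30 in one arm, 0 in the other | 2.83 | 15% |

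**Reading the table.** A balanced count is not enough for zero bias; the deficit has to balance as well. None of the rows is a ceiling, because 8.5 caps replacements at ten and does not cap withdrawals. Nor is ten a forecast for a window of about one day. If withdrawal is unrelated to arm, the bias averages zero over repetitions. In that case, ten withdrawals would split 7:3 or more unevenly (in either direction) with probability 34%, 8:2 or more unevenly with 11%, and 10:0 with 0.2%.

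**The case against.** The strongest reply is that this affects very few patients. The intervention is a single intraoperative exposure, the endpoint follows about a day later, and a patient who leaves the study has usually ended data collection anyway. What clearly remains is investigator withdrawal for medical reasons inside that window, and some of those patients could not complete 40 items. Any trial with a missing outcome falls short of full intention-to-treat. All of this stands, and it is why the point is minor. It does not remove the point: here the outcome is missing by rule, even where the patient could and would answer.

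A second reply concerns blinding. A reader might infer from "The attending anesthetic staff in the operating room is not blinded" that knowledge of the allocation drives withdrawals. The documents do not support that. The same section blinds the surgeons, scrub nurses, nurses giving postoperative care and the endpoint assessor, and most of the window is postoperative. What can be said is only that 8.4 neither defines its medical reasons nor states whether the investigator who withdraws a patient is blinded. An arm-related mechanism is possible but not shown.

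Three other strong readings are tempting.

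- A reader might infer that patients converted to another procedure, or given a rescue bolus, are lost. No section counts either as withdrawal.
- A reader might infer that replaced patients are removed from the analysis. Section 10.1 implies that they stay; 8.5 is merely silent.
- A reader might infer that adverse events go unfollowed. Section 9.4 follows all of them.

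**Conclusion.** The concern holds as a minor point. Followed as written, 8.6 prevents collection of the primary outcome from non-refusing patients withdrawn between envelope opening and 24 hours after extubation, so the analysis in 10.1 cannot be complete for them.

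The likely bias is small: a fraction of a point with a few, roughly even withdrawals, and about 1 to 2 points with ten unevenly split, against a 10-point target. It becomes noticeable (2.6 to 2.8 points, false-positive rate 13% to 15%) only if withdrawals are strongly one-sided or the deficit differs sharply by arm. That judgement rests on the short window and the blinding of most staff, not on any rate in the documents. Nothing here shows that the trial's result would be biased in fact.

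**What to change.** **Section 8.6.** State that, unless the patient refuses further data collection, the QOR-40 and pain scores at 24 and 48 hours and the 4-week contact are still obtained. Record the reason and time of each withdrawal.

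**Sections 8.5 and 10.1.** State that a replaced patient stays in the analysis in the allocated group, and that replacements count as additional patients rather than substitutes. Report withdrawals by arm and reason. For scores that remain missing, that report lets the reader judge the exposure. An imputation with a fixed penalty would rest on an arbitrary number, and I would not require it.

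**Cost.** Wording and a few questionnaires. Table 3 already schedules the QOR-40 and pain scores at 24 and 48 hours. Most patients should still be in hospital at 24 hours: section 1 reports that 45% and 20% of the two groups in the previous trial went home on day 2. The sample size does not change. If ten replaced patients, assumed five per arm, all gave 24-hour scores, 53 per arm would be analysed and t-test power would be 92.5% instead of 89.8%. The limitation is that some medically withdrawn patients may be unable to complete the questionnaire, so a few scores would still be missing.

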8.7 Premature termination of the study

Not applicable.

9. SAFETY REPORTING

9.1 Temporary halt for reasons of subject safety

In accordance to section 10, subsection 4, of the WMO, the investigator will inform the subjects and the reviewing accredited METC if anything occurs, on the basis of which it appears that the disadvantages of participation may be significantly greater than was foreseen in the research proposal. The study will be suspended pending further review by the accredited METC, except insofar as suspension would jeopardise the subjects' health. The investigator will take care that all subjects are kept informed.

9.2 AEs, SAEs and SUSARs

9.2.1 Adverse events (AEs)

Adverse events are defined as any undesirable experience occurring to a subject during the study, whether or not considered related to the components of the intervention group (deep neuromuscular block). All adverse events reported spontaneously by the subject or observed by the investigator or his staff will be recorded.

9.2.2 Serious adverse events (SAEs)

A serious adverse event is any untoward medical occurrence or effect at any dose:

- Results in death
- If life threatening (at any time of the event)
- Requires hospitalization or prolongation of existing inpatients' hospitalization
- Results in persistent or significant disability or incapacity
- Is a congenital anomaly or birth defect
- Any other important medical event that may not result in death, be life threatening, or require hospitalization, may be considered a serious adverse experience when, based upon appropriate medical judgement, the event may jeopardize the subject or may require an intervention to prevent one of the outcomes listed above.

SAEs that result in death or are life threatening should be reported expedited. The expedited reporting will occur not later than 7 days after the coordinating investigator has first knowledge of the adverse reaction. This is for a preliminary report with another 8 days for completion of the report.

9.2.3 Suspected unexpected serious adverse reactions (SUSARs)

Adverse reactions are all untoward and unintended responses to an investigational product related to any dose administered.

Unexpected adverse reactions are SUSARs if the following three conditions are met:

1. the event must be serious (see chapter 9.2.2);
2. there must be a certain degree of probability that the event is a harmful and an undesirable reaction to the medicinal product under investigation, regardless of the administered dose;
3. the adverse reaction must be unexpected, that is to say, the nature and severity of the adverse reaction are not in agreement with the product information as recorded in:
 - Summary of Product Characteristics (SPC) for an authorised medicinal product;
 - Investigator's Brochure for an unauthorised medicinal product.

The sponsor will report expedited the following SUSARs through the web portal *ToetsingOnline* to the METC:

- SUSARs that have arisen in the clinical trial that was assessed by the METC;
- SUSARs that have arisen in other clinical trials of the same sponsor and with the same medicinal product, and that could have consequences for the safety of the subjects involved in the clinical trial that was assessed by the METC.

The remaining SUSARs are recorded in an overview list (line-listing) that will be submitted once every half year to the METC. This line-listing provides an overview of all SUSARs from the study medicine, accompanied by a brief report highlighting the main points of concern.

The expedited reporting of SUSARs through the web portal Eudravigilance or *ToetsingOnline* is sufficient as notification to the competent authority.

The sponsor will report expedited all SUSARs to the competent authorities in other Member States, according to the requirements of the Member States.

The expedited reporting will occur not later than 15 days after the sponsor has first knowledge of the adverse reactions. For fatal or life threatening cases the term will be maximal 7 days for a preliminary report with another 8 days for completion of the report.

In case of a SUSAR in the participating center LUMC, the responsible investigator of LUMC will inform the Radboudumc within the legal terms and the coordinating investigator of Radboudumc will report the SUSAR to the METC.

In case of a SUSAR the anesthesiologist will uncover the randomization.

9.3 Annual safety report

In addition to the expedited reporting of SUSARs, the sponsor will submit, once a year throughout the clinical trial, a safety report to the accredited METC, competent authority, and competent authorities of the concerned Member States.

This safety report consists of:

- a list of all suspected (unexpected or expected) serious adverse reactions, along with an aggregated summary table of all reported serious adverse reactions, ordered by organ system, per study;
- a report concerning the safety of the subjects, consisting of a complete safety analysis and an evaluation of the balance between the efficacy and the harmfulness of the medicine under investigation.

9.4 Follow-up of adverse events

All AEs will be followed until they have abated, or until a stable situation has been reached. Depending on the event, follow-up may require additional tests or medical procedures as indicated, and/or referral to the general physician or a medical specialist.

9.5 Data Safety Monitoring Board (DSMB)

The need for a DSMB is assessed taking the EMEA guidelines on data monitoring committees into consideration. We believe that an interim evaluation does not increase patient safety, because safety of the procedure has already been proven. Study conduct and progress will be monitored according a monitor plan. Thus, a DSMB is not beneficial considering the proposed study design and will therefore not be established

10.1 Primary study parameter(s) and secondary study parameter(s)

For the primary analysis group A and B will be compared with regard to the primary end-point (QOR-40 score at day 1). Factorial ANOVA will be used to compare groups and to adjust for co-variates *i.e.* age, gender and side of nephrectomy. P-values < 0.05 will be considered statistically significant. All analyses will be performed on an intention-to-treat basis.

Study parameters/endpoints	Presentation of data (quantitative/qualitative)
Quality of recovery	Quantitative
Medication use	Quantitative
Pain	Quantitative
Surgical rating score	Quantitative
Nausea/vomiting	Quantitative
Surgical parameters	Quantitative
Evaluation of post-operative complications	Quantitative

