4.4 Sample size calculation

A sample size of 48 patients per group is needed to provide 90% power to detect a 10-point difference in the quality of recovery score at 1 day after extubation (alpha 5%). A 10-point difference represents a minimal relevant difference (8). Based upon our previous study, the standard deviation is 15 points (9).

At the Radboudumc and LUMC, respectively 90 and 45 laparoscopic donor nephrectomies are performed annually. All eligible donors will be screened. With an inclusion rate of approximately 80%, we expect that the screening (and inclusion period) will be 11 months.

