5. TREATMENT OF SUBJECTS

5.1 Investigational treatment

The patient will be randomly assigned to one of the two treatment groups (1:1):

- Deep neuromuscular block/group A
- Moderate neuromuscular block/group B

Intra-operative protocol

- induction with remifentanyl, propofol and rocuronium (intubation dose 0.6 mg/kg). Anesthesia is aimed at a bispectral index score between 45-55. Tracheal intubation is performed 2 minutes after administration of 0.6 mg/kg rocuronium in both groups. In case of a BMI > 30 kg/m² the dose rocuronium will be adjusted taking into account ideal body weight. In group A (deep NMB), an infusion of rocuronium (0.3 to 0.4 mg/kg) is started and titrated towards PTC 0-1. In group B (moderate NMB), no additional rocuronium is administered after tracheal intubation and the neuromuscular function was allowed to recover spontaneously. PTC and TOF measurements every 5 minutes.
- in case of insufficient surgical conditions due to (severe) muscle contractions (SRS 1-2), the protocol allows a 0.6 mg/kg bolus of rocuronium. In case of insufficient surgical conditions (SRS 1 or 2), the surgeon only decides to convert to an open- or hand-assisted procedure if the safety of the patient is compromised.
- pressure-regulated volume-controlled ventilation through an endotracheal tube with a mixture of oxygen in air with 5 cmH₂O PEEP and tidal volume between 6 and 8 ml/kg is used. Minute ventilation is adjusted to main end-tidal carbon dioxide between 31 and 43 mmHg by changing respiratory rate during surgery.
- neuromuscular function will be monitored in a standardized fashion by an acceleromyograph at the wrist (TOF-watch-SX, MIPM GmbH).
- blood loss will be compensated with colloid solution; for 100 ml blood loss, 120 ml colloid solution is given.
- after induction and intubation, patient is positioned in lateral decubitus position
- nasogastric tube for gastric decompression; removed before the end of surgery
- core temperature is measured continuously, aiming at 36-37 C
- no local infiltration of surgical wounds
- the use of drains is avoided
- One hour before the end of the procedure, a loading dose morphine of 0.2mg/kg will be administered.

- In group A, the rocuronium perfusor will be stopped after removal of the trocars.

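### The primary analysis in 10.1 is named as a factorial ANOVA although its aim is covariate adjustment; fitted as named, with all interactions and equal-weight effects, it would fall short of the stated 90% power

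*Combined protocol and SAP*

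**What the plan says.** Section 10.1 compares groups A and B on the QOR-40 at day 1 and states "Factorial ANOVA will be used to compare groups and to adjust for co-variates", listing age, gender and side of nephrectomy. It adds that "P-values < 0.05 will be considered statistically significant" and that analyses follow intention to treat. It gives no age categories, interaction terms, type of sums of squares, or statement of which model term carries the primary test. Section 8.1.3 lists age as a baseline parameter, also without categories.

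Section 4.4 gives the size: "A sample size of 48 patients per group is needed to provide 90% power to detect a 10-point difference", at alpha 5% with a standard deviation of 15 points. It mentions no covariates.

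Section 8.2 randomises in blocks stratified by center only. Table 3 schedules the QOR-40 at -18h as well as at 24h and 48h. Neither center nor the -18h score is among the covariates in 10.1.

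**The concern.** The name of the method and its stated purpose do not match. A factorial ANOVA works on categorical factors and conventionally includes their interactions. To enter as a factor, age would have to be cut into bands. Treatment crossed with gender, side and two age bands gives 2 x 2 x 2 x 2 = 16 cells for 96 donors, an average of 6 per cell. With all interactions and equal-weight effects, the treatment main effect is the unweighted mean of eight within-stratum differences. A stratum with two or three donors per arm then counts as much as one with ten.

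Three things are at stake: precision on the primary endpoint, whether the main effect can be estimated if a cell is empty, and open choices (age cut-points, interactions, sums of squares) on the one test that decides the trial.

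**Working it through.** **Inputs from the documents.** 48 per group, difference 10, SD 15, alpha 5% and power 90% (4.4); 1:1 allocation (5.1). Sidedness is not stated; a two-sided test reproduces 48, whereas a one-sided test would give 39.

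**Assumptions not in the documents.** 45% men, age split at the median, and a less-common-side share varied over 50%, 25% and 15%. Residual SD is held at 15, so the covariates explain nothing.

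**1. The plan's own figure.** n = 2 x (1.96 + 1.2816)^2 x (15/10)^2 = 47.3, so 48 per group. The noncentrality is 10 / (15 x sqrt(2/48)) = 3.27. With 94 error degrees of freedom the noncentral t gives 89.8% power. The stated size reproduces.

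**2. Effect of the number of cells alone.** With 16 exactly balanced cells the variance stays at SD^2 x 2/48 and the error degrees of freedom fall to 96 - 16 = 80. Power is 89.7%. The cell count costs about 0.1 point.

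**3. Effect of unequal cells under equal weighting.** The variance of the treatment main effect is SD^2 x [sum(1/n_A) + sum(1/n_B)] / 8^2, where n_A and n_B are the counts in the eight strata of each arm.

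A hand check with expected counts at a 75/25 side split: each arm has two strata each of 2.7, 3.3, 8.1 and 9.9 donors. The sum of reciprocals per arm is 2 x (0.370 + 0.303 + 0.123 + 0.101) = 1.796. The variance factor is 2 x 1.796 / 64 = 0.0561, against 2/48 = 0.0417, an inflation of 1.35. At 50/50 the strata hold 5.4 or 6.6 donors and the same sum gives an inflation of only 1.01. Chance scatter in the counts adds to this, because nothing in 8.2 balances gender, side or age between arms.

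**4. Simulated cell counts** (power from the noncentral t, averaged over data sets; the equal-weight column covers only data sets without an empty cell):

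| Side split | Mean variance inflation | Crossed, equal-weight | Chance of an empty cell | Same cells, effect pooled | Main effects, age continuous |
|---|---|---|---|---|---|
| 50/50 | 1.24 | about 83% | about 3% | about 87% | about 89% |
| 75/25 | 1.70 | about 70% | about a third | about 87% | about 89% |
| 85/15 | 2.21 | about 59% | about 77% | about 87% | about 89% |

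Check on the 75/25 row: 3.27 / sqrt(1.70) = 2.50, which with 80 degrees of freedom gives 70%.

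**5. Age kept continuous, gender x side x treatment still crossed.** Equal-weight power is about 87%, 73% and 55% for the same three splits. Leaving age unbanded does not by itself remove the loss.

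**6. Possible gain from covariates.** In an additive model with 91 error degrees of freedom, covariates explaining 5% of the outcome variance raise power to about 91%, and 10% to about 92.5%, before any loss from chance imbalance. Adding center and the -18h score to the four terms in 10.1 leaves 96 - 7 = 89 degrees of freedom, which costs almost nothing.

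**The case against.** The strongest reply is that 10.1 never says treatment is crossed with anything. It calls age a covariate and gives adjustment as the purpose, which fits an additive model with continuous age at least as well. On that reading power is about 89% and only the label is wrong. This stands, and it is why the shortfall can be stated only conditionally.

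The large losses also need equal weighting of unbalanced cells. Pooling the effect over the same cells keeps power at about 87% for every side split, and a stratum empty in one arm does not stop the estimate. This stands too. The plan is silent on which would be used.

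A reader might infer that 96 donors in 16 cells are too few, or that 48 per group is wrong. Steps 1 and 2 show neither: the size is right for the two-group test, and balanced cells cost almost nothing. A reader might also infer that every treatment interaction is a further chance of a positive trial. The documents do not support that, since 10.1 names one primary comparison, A versus B, on one endpoint.

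What the reply does not remove is the mismatch. If additive adjustment is meant, the named method is not the one intended; if the named method is meant, it costs power. The same edit is needed either way.

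**Conclusion.** The point holds as a specification fault with a conditional cost. Fitted as named, with all interactions and equal-weight effects, the primary test would have about 83% power at a 50/50 side split, 70% at 75/25 and 59% at 85/15, instead of 90%. These figures rest on assumed gender, side and age splits and on covariates that explain no outcome variance. Under pooling the cost is a few points; under main effects it is about one point, from chance imbalance. No version of the crossed model did better than the main-effects model in these settings. That the trial as planned is underpowered cannot be concluded, because the documents do not fix the model that would make it so. The change is worth making before unblinding.

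**What to change.** Replace the model sentence in 10.1 with wording such as: The primary analysis is a linear model (ANCOVA) of the 24 h QOR-40 with treatment group, gender, side of nephrectomy and center as main effects, and age and the -18h QOR-40 as continuous covariates, with no interaction terms. The single primary test is the treatment coefficient, two-sided at 5%, reported with its 95% confidence interval. Any treatment-by-covariate interaction is exploratory.

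Center belongs in the model because randomisation is stratified by it (8.2). The -18h score is already scheduled (Table 3).

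Cost: a short wording change before unblinding, with no extra patients or data and no change to the 48 per group.
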